## 2. STUDY DESIGN:

Longitudinal (6 month) intervention trial, simple randomized 1:1 with stratification based on age (8-12 years, 13-17 years), non-blinded, to determine if adding the AQI to asthma action plans (AAP) reduces asthma exacerbations, and improves asthma control and quality of life (Figure 3).

Both groups will receive basic education about the AQI including what the AQI is, where to find it, how to use it, and behavioral recommendations by category. In our practice, discussion of the AQI varies by practitioner and patients. While true routine care is likely absence of discussion of the AQI, this was determined to be inappropriate for this study. First, consenting children to the study would result in some discussion of the AQI and therefore bias any true “routine care”. Second, we did not wish to withhold potentially vital asthma self-management to participants. Therefore, all children in the study will receive AQI

[figure not shown]
education. The routine group will receive written AAP only, and the intervention group will receive AAP + AQI written plan. Additionally, the intervention group will be required to download the app onto their or their parent's smartphone (available both for iPhone or android phones) **or** demonstrate the ability to navigate to the airnow.gov website to obtain the AQI at their location. Participants will be followed at monthly intervals for 6 months.

The goal of the AQI is to familiarize persons to their own sensitivities to air pollution and encourage self-modification as needed for personal symptom control. Additionally, there is a goal to prevent discouraging physical activity as most US persons do not meet current daily recommendations.

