### 2.1 Hypothesis and Specific Aims

We hypothesize that the addition of the AQI to AAP will (A) reduce asthma exacerbations, and (B) improve symptom control & quality of life in children with asthma. To test these hypotheses, in this study we will pursue the following specific aims:

- Aim 1: To recruit a pilot cohort of 40 children with asthma. For proof of concept, we will recruit 40 children with asthma from Children's Hospital of Pittsburgh, the only children's hospital serving southwest Pennsylvania (metropolitan area >2.6 million people). Baseline knowledge about the AQI including familiarity, usage, and prior healthcare provider discussion will be assessed.

- Aim 2: To evaluate if the addition of the AQI to AAP reduces asthma exacerbations in a pilot study of children. Participating children (Aim 1) will be randomized to one of two groups. All participants/caregivers will receive an AAP and verbal AQI education. The intervention group will additionally demonstrate the ability to check the AQI, and AQI recommendations will be incorporated onto their written AAP. Children will be followed monthly for 6 months to evaluate adherence to AQI recommendations and assess the frequency of asthma exacerbations, defined per ATS guidelines. Other known factors contributing to asthma exacerbations, such as asthma severity, viral illnesses, allergic triggers will also be monitored.
- Aim 3: To examine whether the addition of the AQI to AAP improves asthma symptom control and quality of life in a pilot study of children. Asthma symptom control will be measured in participating children monthly, and quality of life will be assessed before randomization and at 6 months. Symptom control and quality of life will be evaluated within (before/after intervention) and between groups.

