## STATISTICAL PLAN:

Statistical Analysis: Data will be analyzed using SAS (SAS 9.4, Cary, N.C.). Baseline statistics per treatment group will be obtained. Bivariate analysis of covariates (age, sex, race/ethnicity, asthma severity, phenotype (i.e. atopic), socioeconomic status (SES), exposure to primary or secondary tobacco smoke, FeNO, use of controller medication, etc) between groups will be conducted using student t-test or Wilcoxon rank sum and Fisher's exact or Chi-square (where appropriate and based on distribution). Variables with significant differences between groups ( $P<0.05$ ) will be considered for inclusion in multivariate model selection. The effects of physical activity on the outcomes will be compared between groups. Baseline knowledge and usage of AQI will be assessed. Adherence to AQI will also be assessed and compared between groups, with potential stratification by AQI usage. Additionally, differences in weight and BMI will be assessed to evaluate if adherence to AQI promotes sedentarism and leads to increased weight gain. We will evaluate our outcomes (Aims 2 and 3) in three ways. First, we will evaluate the average difference (overall mean) between groups for our primary outcomes using T test or chi-square (where appropriate). Additionally, we will test the average mean difference between each treatment group by multivariate regression (linear for PAQLQ and ACT or CACT, and/or Poisson or logistic regression for mean asthma exacerbations depending on distribution) to allow for covariate adjustment. Second, we will use paired t-tests (or matched Wilcoxon signed-rank) to evaluate the within group effects (6 month mean – baseline) for each primary outcome. Third, to assess the effects over time in our intervention study (correlated repeat measures data), we anticipate analyzing our primary outcomes by generalized linear mixed models (GLMM). For these models, we will first evaluate the distribution of our primary outcome and determine the most appropriate link (e.g. for severe asthma exacerbations: logistic link if there are overall a high proportion of participants with none, or Poisson link if more consistent with count data). A stepwise approach will be used to build all multivariable models. All final models will include age, sex, race/ethnicity, SES, and tobacco smoke exposure. Additionally, the above outcomes will be stratified by age group (8-12y, 13-17y) to determine if the effects are greater in older children for whom the AQI recommendations may be better self-incorporated into outdoor physical activities, vs the younger group who will likely be more reliant on parental checking and activity modification.

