
Power calculations: Power calculations were conducted using G\*Power 354 and SAS (SAS 9.4, Cary, N.C.) using proc glmpower. For mean difference between treatment groups (routine vs. intervention) with sample size of 20 participants per group, two-tailed test, alpha 0.05, we will have  $\geq 90\%$  power to detect a mean difference of 1.05 between groups for mean asthma exacerbations, ACT and C-CACT, and PAQLQ. Our study will provide  $\geq 80\%$  power to detect a mean difference of 0.91. As the clinical difference for ACT is 2-3 points, we anticipate adequate power to detect a clinical difference. The estimated clinically meaningful difference in PAQLQ is 0.5, and our study may be underpowered to detect this small of difference with this analysis. For comparison within each treatment group, comparing the matched difference (end of study- baseline), using the same assumptions above, we will have  $\geq 90\%$  power to detect a mean difference of 0.76, and  $\geq 80\%$  power to detect a mean difference of 0.66. Therefore, we expect better ability to detect changes in PAQLQ within the groups than between them. For repeat measures, we estimated our power using proc glmpower using F test based on Hotelling-Lawley trace. We estimated a study allocation of 1:1, alpha 0.05, repeated measures at 1, 2, 3, 4, 5 months, lear correlation structure with base correlation 0.85 & decay rate of 1, with an estimated mean difference of 2, standard deviation of 2, which provides a  $\geq 90\%$  power for a treatment group size of 12 for overall mean and n=26 for time\*treatment.

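### The ≥90% power stated for exacerbations is a t-test figure with an unstated SD of 1, and it does not carry over to exacerbation events or counts unless the reduction is very large

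*Combined protocol and SAP*

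**What the plan says.** Section 2.1 sets the size of the study ("To recruit a pilot cohort of 40 children with asthma") and makes fewer exacerbations the first hypothesis and the subject of Aim 2. Section 2.2 defines severe and moderate exacerbations, both of which are events.

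The power paragraph of the Statistical Plan assumes a "sample size of 20 participants per group" and a "two-tailed test, alpha 0.05". It then claims at least 90% "power to detect a mean difference of 1.05 between groups for mean asthma exacerbations, ACT and C-CACT, and PAQLQ", and at least 80% "power to detect a mean difference of 0.91". One pair of numbers thus serves three outcomes on different scales. No SD is given for these figures. No exacerbation rate, proportion with an event or dispersion appears anywhere. The paragraph goes on to compare its figures with a clinical difference of 2 to 3 points for ACT and 0.5 for PAQLQ, so it treats them as raw units. It concedes possible low power for PAQLQ only.

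The analysis paragraph allows a t-test or a chi-square test as the first comparison. It then plans "Poisson or logistic regression for mean asthma exacerbations depending on distribution". For the mixed models it plans, for severe exacerbations, a "logistic link if there are overall a high proportion of participants with none", and otherwise a Poisson link.

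**The concern.** As the sentence reads, the trial has 90% power to detect about one fewer exacerbation per child. A t-test calculation can support that only if the SD of the exacerbation count is known, and the plan does not give one. Event data add a second difficulty. The variance of a count changes with its mean, and the power of a comparison of proportions depends on the control proportion. A single mean difference with no rate behind it therefore does not fix the power of the binary or count analyses.

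Exacerbations carry Hypothesis A and Aim 2. Because the plan warns of low power for PAQLQ alone, a reader would take the exacerbation comparison to be well powered. A non-significant result could then be given more weight than 40 children can support.

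**Working it through.** **Inputs from the documents.** 20 per arm, two-sided alpha 0.05 and the differences 1.05 and 0.91 (Statistical Plan, power paragraph); 1:1 allocation (section 2). **Assumed, because the documents give none:** all control rates, the Poisson form and the dispersion values.

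**1. Reproducing the plan's figures.** Two-sample t-test, 38 df, noncentrality = (difference/SD) × √(20/2).
- With SD = 1, a difference of 1.05 gives 1.05 × 3.162 = 3.32 and power 89.9%. A difference of 0.91 gives 2.88 and power 80.1%.
- The within-group figures behave the same way (paired t-test, 19 df, SD of the change = 1): 0.76 gives 89.7% and 0.66 gives 80.0%.
- All four match, so all four are standardised effects. Read as a raw difference, 1.05 has 58% power if the SD is 1.5 and 37% if it is 2.

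**2. At least one exacerbation (binary).** All 21 × 21 possible tables were enumerated.
- *Complete elimination.* With no events in the intervention arm, Pearson's test needs at least 4 control children with an event and Fisher's test at least 5. From a 20% control proportion, power is P(X ≥ 4) = 59% or P(X ≥ 5) = 37%, with X binomial (20, 0.20). For 90% power the control proportion must be about 30.5% (Pearson) or 36.5% (Fisher).
- *Other reductions:*

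| Control vs intervention | Pearson | Fisher |
|---|---|---|
| 30% vs 15% | 20% | 12% |
| 50% vs 25% | 37.5% | 27% |
| 80% vs 40% | 75% | 65% |
| 60% vs 12% | 92.5% | 87% |
| 70% vs 20% | 91% | 85% |

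**3. Number of exacerbations per child (Poisson).** The arm totals x₁ and x₂ are Poisson with mean 20 × the per-child mean. The score test is z = (x₁ − x₂)/√(x₁ + x₂), with power by enumeration. The t-test on the same counts was simulated.

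| Control vs intervention mean | Score test | t-test |
|---|---|---|
| 0.5 vs 0.25 | 24% | 23% |
| 1 vs 0.5 | 46% | 43% |
| 2 vs 1 | 74% | 72% |
| 3 vs 1.5 | 89% | 88% |
| 1.5 vs 0.45 (difference 1.05) | 94% | 92% |
| 2.0 vs 0.95 (difference 1.05) | 79% | 77% |
| 3.0 vs 1.95 (difference 1.05) | 56% | 54% |

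By the score test, 90% power needs a reduction of 94% at a control mean of 0.5, 76% at 1, 66% at 1.5, 60% at 2 and 50% at 3.

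The difference-of-1.05 rows show why the SD matters. For Poisson counts, an average variance of 1 with a difference of 1.05 requires means summing to 2, which is 1.525 vs 0.475, a 69% reduction. At higher means the variance grows and the same raw difference loses power.

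**4. Overdispersion.** Negative binomial Wald approximation: z = |ln(m₁/m₂)| / √{[(1/m₁ + k) + (1/m₂ + k)]/20}. For 2 vs 1, power is 50% at k = 0.5 and 38% at k = 1. For 2.0 vs 0.95 it is 55% and 42%.

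**The case against.** The strongest reply has four parts.

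- **The t-test is a planned analysis.** A reader might infer that the power was computed for a test that Aim 2 does not use. The analysis paragraph rules that out, because a t-test is one of the two tests named for the first comparison. This part stands. It does not rescue the figure, since the t-test columns above fall as far short as the score test.
- **Read in SD units, the figure roughly holds for counts.** A drop of 1.05 SD from a Poisson mean of 1 is to 0.19, since 0.81/√0.595 = 1.05, and power there is 93% to 95%. From 2 it is to 0.77, with power of 91% to 92%. This also stands, but those are reductions of 81% and about 62%, and the plan does not say that it means SD units.
- **High power is not out of reach.** A reader might infer that 20 per arm cannot give 90% power at realistic rates, or that no effect is detectable when exacerbations are few. The documents give no rates, so the first cannot be shown. Section 2.2 also counts moderate exacerbations, which may raise the control rate. The second is wrong: at a control mean of 0.5, a 94% reduction still reaches 90%.
- **This is a pilot, and the t-test arithmetic is sound.** Both are true. The plan nevertheless makes a positive power claim for exacerbations, and that claim is what needs correcting.

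It is also tempting to test the repeated-measures calculation (difference 2, SD 2) against exacerbations. The plan does not assign it to that outcome, and a difference of 2 fits the quoted ACT difference, so it has no bearing here.

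**Conclusion.** The point holds in this form: the 90% and 80% figures are correct for a t-test on an outcome with SD 1, but as written they are not the power of this design for exacerbations. The unit is unstated, the rate is missing, and the binary and count analyses have no power calculation.

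For a halving, power is 20% to 75% (Pearson) over control proportions of 30% to 80%, and 24% to 89% (Poisson score test) over control means of 0.5 to 3. Ninety per cent is reached only for very large effects, roughly a 60% to 76% reduction at control means of 2 down to 1. Overdispersion lowers the count figures further.

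The reproduction of the plan's figures rests on its own inputs plus SD = 1. Everything beyond that depends on assumed control rates and unadjusted tests with all 40 children analysed.

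**What to change.** In the power paragraph of the Statistical Plan:

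1. Remove exacerbations from the 1.05 and 0.91 statements, or label those figures as SD units and state the SD assumed.
2. Add a short table of detectable effects at 20 per arm for the binary and count analyses, over a stated range of control rates. Cover severe exacerbations and all exacerbations separately, and include an overdispersed case.
3. State that Aim 2 has adequate power only for very large reductions, and that the exacerbation effect will be reported as an estimate with a confidence interval.

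The cost is a few sentences and one table. The stated power for exacerbations becomes less favourable. No more patients, visits or data are needed.

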## 2.2 Outcome Measures

- **Asthma exacerbations** will be defined by ATS guidelines as:
  - (1) Severe:
    - a) requiring 3 or more days of systemic corticosteroids  
**or**
    - b) ED visit/hospitalization for asthma treated with systemic steroids (any duration)
  - (2) Moderate:
    - a) asthma symptoms + increased rescue medication both for at least 2 days  
**or**
    - b) a visit to ED/urgent care/doctor office or clinic for which sick care was sought for asthma but no systemic steroids were given

[figure not shown]
(note: Inclusion of urgent care/doctor office or clinic for acute asthma care is interpretation of PI and not explicitly stated in ATS guidelines, this does not include routine visits)
- **Asthma control** will be defined used validated asthma control tests: ACT for children 12 years and older and CACT for children 8-11 years.
- **Asthma quality of life** will be assessed via the validated pediatric asthma quality of life questionnaire (PAQLQ(S)).

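### The power paragraph gives detectable differences in unlabelled SD units and compares them with raw ACT and PAQLQ points, so its claim of adequate power for ACT is unsupported.

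*Combined protocol and SAP*

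**What the plan says.** The Power calculations paragraph of the Statistical Plan assumes 20 children per group and a two-sided 5% test. For the between-group comparison it claims at least 90% "power to detect a mean difference of 1.05 between groups for mean asthma exacerbations, ACT and C-CACT, and PAQLQ", and at least 80% power for 0.91. No SD or unit accompanies these figures.

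It then turns to clinical differences in points. For ACT: "As the clinical difference for ACT is 2-3 points, we anticipate adequate power to detect a clinical difference". For PAQLQ, where the stated clinical difference is 0.5, it says "our study may be underpowered to detect this small of difference with this analysis".

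For change within a group it gives 0.76 (90% power) and 0.66 (80%), and concludes: "Therefore, we expect better ability to detect changes in PAQLQ within the groups than between them".

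The only SD in the paragraph belongs to a later repeated-measures calculation, "with an estimated mean difference of 2, standard deviation of 2", which names no outcome. That calculation reports at least 90% "power for a treatment group size of 12 for overall mean and n=26 for time" by treatment.

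Section 2.2 assigns the control instruments by age: "ACT for children 12 years and older and CACT for children 8-11 years". The analysis text describes the regression as "linear for PAQLQ and ACT or CACT" and does not say whether the two scores are pooled.

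**The concern.** Exacerbation counts, ACT, C-ACT and PAQLQ are on different scales. One detectable difference can serve all of them only if it is expressed in SDs. The paragraph calls the figures mean differences and reads them against clinical thresholds in points.

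Read as points, 1.05 makes a 2-3 point ACT difference look two to three times what the trial can detect with 90% power. Whether that is so depends on an ACT SD that the plan never gives. Without it, a reader of a null result cannot tell which ACT or PAQLQ differences this pilot could have detected.

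**Working it through.** **Inputs (Power calculations paragraph).** n = 20 per group; two-sided alpha 0.05; between-group figures 1.05 and 0.91; within-group figures 0.76 and 0.66; clinical differences of 2-3 points (ACT) and 0.5 (PAQLQ); SD 2 in the repeated-measures calculation only.

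**1. Reproducing the plan's figures.** Exact noncentral-t power, with d = difference / SD:

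- Two-sample: df = 38, noncentrality = d × √(20/2).
- Paired: df = 19, noncentrality = d × √20, with d in units of the SD of change.

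| Test | Plan's figure | Power if SD = 1 | Exact d for the target |
|---|---|---|---|
| Between groups, 90% | 1.05 | 89.9% | 1.052 |
| Between groups, 80% | 0.91 | 80.1% | 0.909 |
| Within group, 90% | 0.76 | 89.7% | 0.764 |
| Within group, 80% | 0.66 | 79.9% | 0.660 |

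All four agree to rounding, so the arithmetic is sound in SD units. They are not points at the paragraph's own SD of 2: raw between-group differences of 1.05 and 0.91 would then be d = 0.525 and 0.455, with 37% and 29% power.

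**2. ACT in points.** Detectable difference = 0.909 × SD (80%) or 1.052 × SD (90%). The largest SD that still gives the stated power is:

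- 80%: 2/0.909 = 2.20 for 2 points; 3/0.909 = 3.30 for 3 points.
- 90%: 2/1.052 = 1.90 for 2 points; 3/1.052 = 2.85 for 3 points.

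| ACT SD | Power, 2 points | Power, 3 points |
|---|---|---|
| 2 | 87% | >99% |
| 3 (assumed) | 54% | 87% |
| 4 (assumed) | 34% | 64% |
| 5 (assumed) | 23% | 46% |

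Here SD means the SD of whatever ACT summary is compared between the groups.

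**3. PAQLQ, 0.5 points.** 80% power between groups needs SD ≤ 0.5/0.909 = 0.55. Within a group it needs SD of change ≤ 0.5/0.660 = 0.76. With an SD of 1 (assumed), between-group power is 34%.

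**4. Within versus between groups.** The figure 0.66 is in SDs of change and 0.91 in SDs of score. With equal SDs at both times and correlation r, SD of change = SD × √(2(1 − r)). The within-group detectable difference is the smaller one when 0.660 × √(2(1 − r)) < 0.909, that is, when r exceeds about 0.05. The direction of the plan's sentence therefore probably holds, but the printed figures are not comparable.

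**5. Two instruments.** Unless every enrolled child falls on one side of the age cut, neither ACT nor C-ACT has 20 per group. If the scores are analysed separately with 8 to 12 per group on one instrument (assumption), the 80%-power effect is 1.51 to 1.20 SD instead of 0.91.

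**6. Repeated measures (secondary).** The mean profile over visits is not given, nor whether 26 is per group or total, so the stated sizes cannot be checked directly. Suppose 2 is the average difference over visits. The stated correlation structure (base 0.85, decay 1, months 1-5) gives correlations from 0.85 down to 0.7225 and a matrix mean of 0.845. The SD of a child's mean is then 2 × √0.845 = 1.84, and the effect is 2/1.84 = 1.088. Power is 72% at 12 per group, 90% at 19 and 92% at the planned 20. Twelve per group would need an average difference of about 2.55 for 90%. Adding month 6 gives 72.5% at 12 per group. The time-by-treatment figure can be neither confirmed nor refuted.

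**The case against.** The strongest reply is that this is a 40-child proof-of-concept pilot, that nothing in the documents derives 40 from this paragraph, and that correcting units changes no sample size, visit or endpoint. That stands, and it limits the severity. But the plan still makes an explicit power claim that readers will use to interpret the results.

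Second, at the only SD the plan states (2), the ACT sentence survives at the 80% level: the detectable difference is 0.91 × 2 = 1.82 points, and power for 2 points is 87%. At 90% it is 1.05 × 2 = 2.1 points, just above the lower clinical limit. This is why the conclusion is called unsupported and not false. The SD of 2 is tied to no outcome, and the larger SDs in the table are assumptions.

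Third, ACT is collected monthly. If the comparison uses each child's average over visits, the plan's correlations make the SD of that average 1.84/2 = 0.92 of a single-visit SD. The 80% limits, in single-visit SD, then rise to 2.20/0.92 ≈ 2.4 and 3.30/0.92 ≈ 3.6. That is a fair refinement, but it still needs a stated SD.

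Fourth, the within-group sentence is probably right in direction, the PAQLQ caveat may well be right, and the repeated-measures target appears to be met at 20 per group. All of this is accepted. For those sentences the fault lies in units and missing inputs, not in a demonstrated wrong conclusion. The age split between instruments is likewise not documented, so the 8-12 range is only illustrative.

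**Conclusion.** The concern holds. The four figures are standardized effects presented as mean differences and then compared with points. The claim of adequate power for ACT is unsupported as written: it is met at 80% power for 2 points only if the SD is at most 2.2, and for 3 points only if it is at most 3.3. Depending on an SD the plan does not give, power for 2 points runs from 87% (SD 2) to 23% (SD 5, assumed). All of these figures assume 20 analysed children per group on a common score; the paragraph makes no allowance for dropout. The PAQLQ statements share the unit fault, though their direction may be right. The repeated-measures sizes are a secondary reporting gap. This should be fixed, but it does not threaten the design.

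**What to change.** - Relabel the figures as 1.05 and 0.91 SD between groups, and 0.76 and 0.66 SD of change within groups.
- For each outcome, state an assumed SD with a range and its source, plus a baseline-to-end correlation for the within-group test, and convert to points. For ACT, say whether the SD refers to one visit or to the average over visits.
- Replace the ACT adequacy sentence with power at 2 and 3 points across the SD range.
- Say whether ACT and C-ACT are pooled, and how many children per group each is expected to have.
- Restate both PAQLQ sentences in common units, keeping the caveat about low power if it still holds.
- Rerun the repeated-measures calculation at 20 per group over follow-up visits V2-V7. Report power for the overall mean and for time-by-treatment, give the mean profile, and say whether 12 and 26 are per group or total.

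The cost is one rewritten paragraph and a rerun of the power software. No patients, visits or endpoints are added. The stated power may become less favourable.

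### The ≥90% power claimed for time-by-treatment does not follow from the stated mean difference of 2 and is silent on a sustained benefit; the companion group size of 12 for the overall mean gives 72%

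*Combined protocol and SAP*

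**What the plan says.** Section 2.1 states the hypothesis as a difference in level between arms: "We hypothesize that the addition of the AQI to AAP will (A) reduce asthma exacerbations, and (B) improve symptom control & quality of life".

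The Statistical Analysis paragraph of the Statistical Plan lists three routes for Aims 2 and 3. The first compares group means, with adjusted regression, and the second looks at change within each group. The third is the mixed model (GLMM): "Third, to assess the effects over time in our intervention study (correlated repeat measures data), we anticipate analyzing our primary outcomes by generalized linear mixed". The paragraph does not say which model term is the test.

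The Power calculations paragraph treats the between-group comparison first, "with sample size of 20 participants per group, two-tailed test, alpha 0.05". For the repeated measures it says "we estimated our power using proc glmpower using F test based on Hotelling-Lawley trace". The inputs are:

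- Design and time points: "We estimated a study allocation of 1:1, alpha 0.05, repeated measures at 1, 2, 3, 4, 5 months"
- Correlation between months: "lear correlation structure with base correlation 0.85 & decay rate of 1"
- Size of effect and spread: "with an estimated mean difference of 2, standard deviation of 2"

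From these inputs the paragraph draws its conclusion: "which provides a $\geq 90\%$ power for a treatment group size of 12 for overall mean and n=26 for time\*treatment". No monthly means by arm are given, and the text does not say whether 26 is per group or in total.

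**The concern.** All five time points in the power set-up fall after randomisation. Over those months the time-by-treatment null is that the arm difference is the same at every month. A benefit that is present by month 1 and persists satisfies that null exactly, however large it is. A single mean difference cannot determine the power of such a test; only a month-by-month profile can.

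The power paragraph is the only place that names candidate mixed-model terms, and it presents time-by-treatment as one of two powered tests. If that term were read as the test of whether the intervention works, a real and sustained effect would give a non-significant result about 95% of the time. A significant result would show only that the effect changed, which includes a benefit that fades.

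**Working it through.** **Inputs**, all from the Power calculations paragraph: alpha 0.05, 1:1 allocation, months 1 to 5, SD 2, mean difference 2, LEAR correlation with base 0.85 and decay 1, Hotelling-Lawley F test. The planned size is 20 per group (40 children, section 2.1).

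**Correlations.** At lag d the exponent is 1 + (d − 1)/3. This gives 0.85, 0.805, 0.763 and 0.7225 at lags 1 to 4. The covariance matrix S is 4 times this correlation matrix.

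**Formula.** With n per group, monthly arm differences θ and p contrasts U:

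λ = (n/2) · (U′θ)′ (U′SU)⁻¹ (U′θ), referred to a noncentral F with p and 2n − 2 − p + 1 df.

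**Overall mean (p = 1), the plan's own figure first.** The 25 correlations sum to 5 + 2(4×0.85 + 3×0.805 + 2×0.763 + 0.7225) = 21.13. The variance of a child's five-month mean is 4 × 21.13/25 = 3.38, an SD of 1.84. Then λ = (n/2) × 2²/3.38.

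| n per group | λ | Power |
|---|---|---|
| 12 (stated) | 7.10 | 72% |
| 18 | 10.65 | 89% |
| 19 | 11.24 | 90% |
| 20 (planned) | 11.83 | 92% |

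The stated 12 is not reproduced. Because this test sees only the five-month average, any profile averaging 2 gives the same 72%. Other readings at 12 per group give 75% (AR(1)), 70% (compound symmetry) and 83% (one-sided). Reading the printed SD of 2 as a variance gives 95%, but that is not what the text says.

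**Time-by-treatment (p = 4, contrasts between months).** With θ = (2, 2, 2, 2, 2) every contrast is zero, so λ = 0 and power equals alpha at any n. Simulation agrees: 5.1% rejected at 20 per group, 4.8% at 26 and 5.4% at 500. For linear profiles from month 1 to month 5:

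| Arm difference, month 1 → 5 | 20 per group | 26 per group |
|---|---|---|
| 2 → 2 | 5% | 5% |
| 1 → 2 | 33% | 44% |
| 0.4 → 2 | 75% | 87.5% |
| 0 → 2 | 92% | 98% |
| 2 → 0 (fading) | 92% | 98% |

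Profiles that all average exactly 2 give 11% (1.75 → 2.25), 33% (1.5 → 2.5) or 92% (1 → 3) at 20 per group. So a mean difference of 2 does not fix this test's power. For 90%, a linear profile must change by 1.66 points between months 1 and 5 at 26 per group, by 1.92 at 20 per group, and by 2.50 if 26 is a total (13 per group).

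With six follow-up visits (V2 to V7) and a constant difference of 2, the picture at 20 per group is the same: overall mean 92%, interaction 5%.

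**Illustration only, for exacerbations.** The assumptions here are not from the documents and were not varied: 0.35 events per month in controls, between-child gamma variance 0.7, V2 to V7, 20 per arm, 400 runs, and a GEE Poisson model with linear month rather than the planned mixed model. A constant rate ratio of 0.3 was detected in 88% of runs by the arm term and 5.5% by arm-by-month; a ratio of 0.5 gave 47.5% and 5.5%. With no effect, the arm term rejected in 7.0% and the interaction in 5.8%. The conclusion does not rest on this.

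**The case against.** **A reader might infer that the ≥90% figure is false and that the true power is 5%.** The documents do not support that. They never call the difference steady. A constant difference yields no finite sample size, so a reported 26 implies that some non-constant profile was entered. Some such profiles do exceed 90%: 0 → 2 gives 98% at 26 per group, and a one-df linear-trend test of that profile needs 13 per group, 26 in total. This part of the objection stands. What remains is that the profile is not stated, so the figure cannot be checked.

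**A reader might also infer that the problem is unavoidable for exacerbations**, because the shortened respiratory questionnaire starts only at V2 (Tables 1 and 2). That is not established. V1 includes an intake respiratory questionnaire whose items are not shown, and the second analysis route contrasts six-month values with baseline for every primary outcome.

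**Baseline could change what the interaction tests.** ACT and C-ACT are collected at V1. If V1, with zero difference, were a repeated measure, the interaction would carry the treatment effect, with 99.8% power at 20 per group. The power set-up does not include V1. It also omits month 6, so it does not by itself define the analysis dataset.

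**The level difference is already tested.** The first route compares group means and is powered first. No passage makes time-by-treatment the deciding test, and nothing shows that it set the sample size. This limits the harm to the mixed-model route. It does not repair a power statement that fails to follow from its inputs, nor settle which model term will count.

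**Conclusion.** The point holds as a mismatch between a stated power and its stated alternative, for both repeated-measures figures.

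- **Time-by-treatment, n = 26:** power at the planned 20 per group runs from 5% to 92% across the profiles from 2 → 2 to 0 → 2, and the plan does not say which it assumes. Whatever profile lies behind 26, the figure gives no assurance about a sustained benefit, which this test cannot detect over post-randomisation months.
- **Overall mean, group size 12:** the printed inputs give 72%, not ≥90%. The planned 20 per group gives about 92%, so the design itself is not undermined for a five-month average difference of 2 with SD 2.

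These results rest on the plan's correlation, SD and time points, complete data, and the Hotelling-Lawley F. The claim is not that 90% is unattainable for the interaction, nor that the first two analysis routes are affected.

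**What to change.** 1. **Statistical Analysis paragraph.** State that the mixed-model test for Aims 2 and 3 is the arm effect averaged over the follow-up visits, for outcomes collected monthly. Report arm-by-month as a description of onset or fading, not as evidence for or against benefit.
2. **Power calculations paragraph.** Replace the repeated-measures claim with: *With a difference of 2 at every month, the overall-mean test has about 92% power at 20 per group; time-by-treatment has no power against a constant difference.*
3. **Interaction figure.** Either drop it, or give the monthly differences it assumes, say whether 26 is per group or total, and restate its power at 20 per group.

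The cost is wording only, with no new data or participants. The downside is giving up a formal powered claim about change in the effect over time. At 20 per group that claim reaches 90% only for steep profiles (a linear change of about 1.9 points over months 1 to 5).
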